5 STUDY POPULATION CHARACTERISTICS

5.1 Subject disposition

Summaries of the disposition of subjects (for all subjects enrolled in PS0011) as well as the subjects who discontinued due to AEs (for the FAS) will be produced based on the PS0011 treatment group. The disposition of subjects for all subjects enrolled will include the number of subjects included in each analysis set (FAS, SS and PK-PPS) overall and by site.

In addition, the number and percentage of subjects who discontinued the study, including a breakdown of the main reasons for discontinuation, will be presented for subjects in the FAS.

5.2 Protocol deviations

A summary, using the ES, of the number and percentage of subjects with an important protocol deviation (including a summary of subjects excluded from the PK-PPS due to important protocol deviations) by PS0011 treatment group, overall and by type of deviation will be provided.

If the dosing for a visit is +/- 7 days out of window, then the plasma concentration from that visit and all subsequent visits will be excluded from the PK summary. The number and percentage of subjects with at least one measurement excluded from the PK analysis will be summarized by PS0010/PS0011 treatment group.

A by-subject listing of important protocol deviations will be provided.

6 DEMOGRAPHICS AND OTHER BASELINE CHARACTERISTICS

Unless specified otherwise, all summaries detailed in this section will be performed on the SS, where Baseline is defined relative to PS0010.

6.1 Demographics

Demographic variables will be summarized by PS0011 treatment group and overall.

The following continuous variables will be summarized using descriptive statistics (number of subjects, mean, SD, median, minimum and maximum):

- Age at the time of study entry (years)

- Weight (kg)
- Height (cm)
- BMI (kg/m²)

BMI (kg/m²) will be calculated as:

$$\text{BMI} = \frac{\text{Weight}}{\text{Height}^2} \quad (1)$$

where weight is given in kg and height is given in m.

The following categorical variables will be summarized using frequency counts and percentages:

- Age group (≤ 18 years, 19 to < 65 years, ≥ 65 years)
- Age group (18 to < 65 years, 65 to < 85 years, ≥ 85 years)
- Age group (< 40 years, 40 to < 65 years, ≥ 65 years)
- Gender
- Race
- Ethnicity
- Weight (< 100 kg, ≥ 100 kg)
- BMI (< 25 kg/m², 25 to < 30 kg/m², ≥ 30 kg/m²)

By-subject listings of demographics will be provided.

6.2 Other Baseline characteristics

Baseline characteristics (including Baseline clinical measurements) will be summarized by PS0011 treatment group and overall.

The following continuous variables will be summarized using descriptive statistics (number of subjects, mean, SD, minimum, median and maximum):

- Psoriasis BSA (%)
- Duration of disease (years)
- PASI score
- DLQI total score.

Duration of disease (years) will be calculated as:

Duration of disease

$$= \frac{(\text{Date of informed consent} - \text{Date of onset of plaque psoriasis}^1)}{365.25} \quad (2)$$

¹If the date of onset of plaque psoriasis is partial, it should be imputed to the most feasible date (ie, last day of the month if only day is missing, or the last day of the year if day and month are missing).

The following categorical variables will be summarized using frequency counts and percentages:

- Duration of disease (<median, ≥median)
- Region (North America [Canada, USA], Europe and Asia [Czech Republic, Hungary, Poland, Japan])
- Country
- Prior systemic phototherapy or chemophototherapy (yes, no)
- Prior nonbiologic systemic therapy (yes, no)
- Prior biologic systemic therapy (yes, no)
- Prior anti-TNF therapy (yes, no)
- Any prior systemic therapy (yes, no)
- PASI score (<20, ≥20)
- Psoriasis BSA (<20%, ≥20%)
- IGA score (0, 1, 2, 3, 4).

6.3 Medical history and concomitant diseases

All medical history will be listed and the number and percentage of subjects with any medical history will be summarized by PS0011 treatment group, SOC and PT.

6.4 Prior and concomitant medications

Medication start and stop dates will be compared to the date of first dose of both PS0010 and PS0011 treatments to allow medications to be classified as either Prior or Concomitant.

Prior medications include any medications that started prior to the start date of study medication. Concomitant medications are medications taken at least one day in common with the study medication dosing period.

Details of imputation methods for missing or partial dates are described in [Section 4.2.1](#).

The number and percentage of subjects taking Prior medications (excluding past psoriasis medications) will be summarized by PS0011 treatment group, overall and by ATC class, presenting Anatomical Main Group (ATC Level 1), Pharmacological Subgroup (ATC Level 3), and preferred term.

The number and percentage of subjects taking Concomitant medications will be summarized similarly.

A by-subject listing of all Prior and Concomitant medications will be provided.

7 MEASUREMENTS OF TREATMENT COMPLIANCE

All summaries detailed in this section will be performed on the SS.

Due to the method of administration of the treatments, compliance will be examined in terms of completed injections, where two injections will be considered as one complete treatment administration (ie, one dose).

Treatment compliance will be calculated as:

$$\text{Treatment compliance} = \frac{\text{total number of completed injections}}{\text{total number of expected injections}} \times 100 \quad (3)$$

where the total number of expected injections is derived relative to when the subject finishes treatment. If a subject completes treatment, 24 injections are expected (two at each Q4W). If a subject discontinues early, then the number of expected injections is based on the time of early discontinuation relative to the dosing visits.

A summary of percent treatment compliance categorized as $\leq 80\%$ and $> 80\%$ will be provided by PS0011 treatment group.

A by-subject listing of treatment compliance will be provided.

8 SAFETY ANALYSES

All safety summaries and listings will be performed using all subjects in the SS.

8.1 Statistical analysis of the primary safety variable

8.1.1 Derivation of TEAEs

An AE is any untoward medical occurrence in a subject or clinical investigation subject administered with a pharmaceutical product that does not necessarily have a causal relationship with this treatment. An AE can therefore be any unfavorable and unintended sign (including an abnormal laboratory finding), symptom, or disease temporally associated with the use of a medicinal (investigational) product, whether or not related to the medicinal (investigational) product.

TEAEs are defined as those AEs that have a start date on or following the first administration of study treatment in PS0011 through the final administration of study treatment + 140 days (covering the 20-week SFU period). If it is not possible (due to partial dates) to determine whether or not an AE is treatment-emergent then it will be assumed to be a TEAE. TEAEs will be categorized to the treatment group based on the dose being received at the time of onset of the event.

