14.3 Planned safety analyses

Safety variables will be analyzed for all subjects in the SS.

Adverse events will be coded according to the Medical Dictionary for Regulatory Activities (MedDRA[®]). Treatment-emergent AEs will be defined as events that have a start date on or following the first administration of study treatment in PS0011 through the final administration of study treatment +140 days (covering the 20-week SFU Period). Treatment-emergent AEs will be categorized by PS0011 treatment group. Tables will include columns for placebo, bimekizumab 64mg Q4W, bimekizumab 160mg Q4W, bimekizumab 320mg, and All bimekizumab (ie, any dose of bimekizumab).

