- **Bimekizumab 160mg Q4W to Bimekizumab 160mg Q4W** – Subjects randomized to bimekizumab 160mg Q4W or bimekizumab 320mg loading dose + 160mg Q4W in PS0010 who achieve PASI90 response at Week 12 of PS0010 and continue to receive bimekizumab 160mg Q4W in PS0011. Note that the PS0010 160mg Q4W groups with and without the loading dose are combined here.
- **Bimekizumab 160mg Q4W to Bimekizumab 320mg Q4W** – Subjects randomized to bimekizumab 160mg Q4W or bimekizumab 320mg loading dose + 160mg Q4W in PS0010 who do not achieve PASI90 response at Week 12 of PS0010 and are treated with bimekizumab 320mg Q4W in PS0011. Note that the PS0010 160mg Q4W groups with and without the loading dose are combined here.
- **Bimekizumab 320mg Q4W to Bimekizumab 320mg Q4W** – Subjects randomized to bimekizumab 320mg Q4W in PS0010 and continue on 320mg Q4W in PS0011. No distinction will be made between subjects that were or were not PASI90 responders at Week 12 of PS0010.
- **Bimekizumab 480mg Q4W to Bimekizumab 320mg Q4W** – Subjects randomized to bimekizumab 480mg Q4W in PS0010 and continue on 320mg Q4W in PS0011. No distinction will be made between subjects that were or were not PASI90 responders at Week 12 of PS0010.

The treatment groups to be used in the presentations of safety and efficacy will depend on the objective of the summaries and will be specified accordingly.

Change #98

Section 14.2 Planned safety analyses (now Section 14.3)

Adverse events will be coded according to the Medical Dictionary for Regulatory Activities (MedDRA[®]). Treatment-emergent AEs will be defined as events that have a start date on or following the first administration of study treatment in PS0011 through the final administration of study treatment +119 days (covering the 17-week SFU Period). Treatment-emergent AEs will be categorized to treatment group based on the dose being received at the time of onset of the event. Tables will include columns for bimekizumab 320mg Q4W, bimekizumab 160mg Q4W, and All bimekizumab (ie, either dose of bimekizumab).

Change from Baseline variables will be defined relative to the Baseline measurement from PS0010.

Has been changed to:

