1 INTRODUCTION

This statistical analysis plan (SAP) defines the summary tables, figures, and listings to be generated for the clinical study report and is based on the protocol amendment 1 (12 Aug 2016).

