3.6 Treatment assignment and treatment groups

At Baseline, eligible subjects will be assigned as described in [Section 2.3.2](#). Summaries using the FAS will be based on treatments according to the assignment and not actual treatment received.

It is expected that subjects will receive treatment as assigned. Hence, safety analyses should be based on assigned treatment for the SS. However, if it is determined after unblinding that subjects assigned to placebo received bimekizumab at any time, then these subjects will be reallocated to the appropriate bimekizumab group and will be summarized accordingly from the time point at which the misallocation occurred. If a subject receives different doses of bimekizumab at different time points, then the subject will be allocated to the highest dose received. If the highest dose was received earlier than the other(s), then all safety data will be summarized under that dose. If the highest dose was received later than the other(s), then safety data will be summarized under that dose starting from the time point at which it was first received. Since the period of exposure at risk includes an additional 140 days following the last dose of study medication, no consideration is given to the time at which exposure to misallocated doses can be considered complete.

Subjects assigned to a bimekizumab group will only be reallocated to the placebo treatment group if they never received bimekizumab.

Because subjects entering PS0011 may or may not be continuing on the same dose as that received in PS0010, there are various combinations of treatment that could be received when considering both PS0010 and PS0011 together. For describing the summaries to be produced, treatment groups will be categorized as either the PS0011 treatment groups or PS0010/PS0011 treatment groups. The categorizations are outlined below.

PS0011 treatment groups

This refers to the study treatment assigned to the subject at the beginning of PS0011 and does not account for the treatment received in PS0010. The PS0011 treatment groups are as follows:

- Placebo
- Bimekizumab 64mg Q4W
- Bimekizumab 160mg Q4W
- Bimekizumab 320mg Q4W
- All Bimekizumab (optional – to be used only if specified)

PS0010/PS0011 treatment groups

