3.11 Changes to protocol-defined analyses

There have been no changes to the protocol-defined analyses.

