8.1.6 Analysis of the primary safety variable

All TEAEs will be summarized descriptively by PS0011 treatment group, primary SOC, HLT, and PT. This summary will include the number and percentage of subjects experiencing the event, the number of events, EAIR with associated 95% confidence interval based upon the Chi-Square distribution (Ulm, 1990), and the EAER.

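### SAP 8.1.1 attributes TEAEs to the dose at onset, against protocol 14.3 and SAP 8.1.6; the effect is confined to certain misdosed subjects, whose time at risk SAP 8.1.3 also leaves undivided

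*SAP*

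**What the plan says.** Four places in the current documents decide which column a treatment-emergent event enters.

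- Protocol 14.3: "Treatment-emergent AEs will be categorized by PS0011 treatment group". Protocol 14.2 and SAP 3.6 define that group alike; in the SAP's words, "This refers to the study treatment assigned to the subject at the beginning of PS0011 and does not account for the treatment received in PS0010".
- SAP 8.1.1: "TEAEs will be categorized to the treatment group based on the dose being received at the time of onset of the event".
- SAP 8.1.6, the primary safety analysis: "All TEAEs will be summarized descriptively by PS0011 treatment group, primary SOC, HLT, and PT".
- SAP 3.6: the Safety Set is analysed by assigned treatment, with exceptions for misdosing. A placebo subject given bimekizumab moves to the bimekizumab group from that point. A subject given different bimekizumab doses goes to the highest: "If the highest dose was received earlier than the other(s), then all safety data will be summarized under that dose"; if it came later, the move takes effect from its first receipt. A bimekizumab subject moves to placebo only if bimekizumab was never given. A misallocated dose is not treated as having ended.

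SAP 8.1.3, equation (7), sets exposure at risk as last dose minus first dose plus 140 days, one total per subject. SAP 3.11 says "There have been no changes to the protocol-defined analyses".

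**The concern.** The 8.1.1 sentence governs the numerator of the primary safety variable and disagrees with the protocol section it implements. Its likely source is visible in the protocol's amendment log, where the superseded text for the open-label design reads "Treatment-emergent AEs will be categorized to treatment group based on the dose being received at the time of onset of the event". That rule suited a design in which the investigator could change the dose during the study. Amendment 1 removed those changes and moved to the PS0011 treatment group, yet the SAP, which says it follows Amendment 1, still carries the old sentence.

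At stake is the rate by dose. If a programmer places events by 8.1.1 and person-time by 3.6, the exposure-adjusted incidence rate (EAIR) can combine an event from one group with time from another. Only PASI90 responders remain on placebo or 64mg, so those columns may be small enough for a single event to matter.

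**Working it through.** **Time at risk.** SAP section 7 expects 24 injections from a completer, two per dose, so 12 doses; the last is at Week 44, day 11 × 28 = 308. Equation (7) gives 308 + 140 = 448 days, or 448/7 = 64 weeks. This reproduces the maximum duration in protocol 5.1.1.

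**Where 8.1.1 and 3.6 differ.** Each of the 448 days was assigned to a column under both rules. The dosing sequences are hypothetical. Three readings are assumed: under 8.1.1 the last dose carries through the 140 days; under 3.6 a highest dose given mid-study applies from first receipt onward; and data before that point stay under the dose actually received.

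| Assigned; received | Days that differ |
|---|---|
| 160mg; as assigned | 0 |
| 160mg; 320mg at Baseline, then 160mg | 420 (448 − 28) |
| 160mg; one 320mg dose at Week 12, then 160mg | 336 (448 − 112) |
| Placebo; one 160mg dose at Week 12, then placebo | 336 (448 − 112) |
| 320mg; one 160mg dose at Week 12, then 320mg | 28 (Week 12 to Week 16) |
| 160mg; one placebo dose at Week 12, then 160mg | 28 (Week 12 to Week 16) |
| Placebo; 160mg from Week 12 on | 0 |
| 160mg; 320mg from Week 12 on | 0 |
| 160mg; placebo throughout | 0 |

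Every row that differs has a dose lower than one already received. In the second row, 3.6 places everything under 320mg, 8.1.1 places events after the Week 4 dose under 160mg, and equation (7) gives one total that 3.6 puts under 320mg. A later event is then in one column and its time in the other.

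**Effect on a rate.** Equation (10): EAIR = 100n / total subject-years. Take the placebo subject with one 160mg dose at Week 12 (day 84) and an event on day 210, with no other events in the column. The column size is not in the documents; 3 to 10 is assumed, and all others contribute 448 days.

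- Event and time both by 3.6: the event leaves placebo, and placebo EAIR = 0.
- Event by 8.1.1, time by 3.6, column of 3: (2 × 448 + 84)/365.25 = 2.68 years; 100/2.68 = 37.3 per 100 subject-years (95% CI 0.9 to 207.7).
- The same, column of 10: (9 × 448 + 84)/365.25 = 11.27 years; 8.9 (0.2 to 49.4).
- Event and time both by assignment: 100 × 365.25/(2 × 448 + 210) = 33.0 for 3 subjects; 100 × 365.25/(9 × 448 + 210) = 8.6 for 10.

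Most of the difference comes from where the event is placed. Mixing the rules for events and time accounts for 37.3 against 33.0, or 8.9 against 8.6.

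**The separate gap in 8.1.3.** For a placebo subject given 160mg from Week 12 on, 8.1.1 and 3.6 agree about events. SAP 3.6 implies 84 days in placebo and 448 − 84 = 364 days in 160mg. Equation (7) returns 448 days with no division, so whichever column receives the total, the other loses its share. Correcting 8.1.1 does not cure this.

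**The case against.** The best defence is that nothing happens in practice. PS0011 has one fixed assignment per subject, so dose at onset equals PS0011 treatment group for everyone dosed correctly. SAP 3.6 expects subjects to receive treatment as assigned, and neither document reports misdosing. Sections 3.6, 8.1.6 and 8.2.1 all name the PS0011 group, and a programmer would probably follow them over one leftover sentence. The analysis is descriptive, with no tests. All of this stands as to size; it does not reconcile 8.1.1 with protocol 14.3.

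Three stronger readings are tempting, and the documents do not support them.

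- A reader might infer that every misdosed subject is affected. Subjects who move up and stay there, or who are assigned bimekizumab and receive only placebo, are placed alike by 8.1.1 and 3.6.
- A reader might infer that events in the safety follow-up have no column because no dose is then being received. The same paragraph of 8.1.1 runs TEAEs to 140 days after the last dose and says this covers the follow-up, so carrying the last dose forward is the natural reading.
- A reader might treat SAP 3.6 as another departure from the protocol. Protocol section 14 gives no rule for misdosing and leaves detail to the SAP, so 3.6 is better read as an elaboration.

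The amendment log is used here only to explain where the sentence probably came from. The contradiction lies between texts now in force.

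**Conclusion.** Wrong as written, low impact. The conflict of SAP 8.1.1 with protocol 14.3 and SAP 8.1.6 is certain from the wording, and SAP 3.11 does not disclose it. Its effect on results is nil for correctly dosed subjects and conditional for the rest: a subject must receive less than a dose already received, and an event must fall on a day when the rules differ. Switches between bimekizumab doses leave the All bimekizumab column unchanged; only switches involving placebo can reach it. The undivided exposure in 8.1.3 is a real second gap, also limited to misdosed subjects. The day counts and rates above are illustrations on assumed dosing sequences, event day and column sizes. They do not estimate what occurred in PS0011.

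One assumption matters at the margin. SAP 3.6 does not say where data collected before the first receipt of the highest dose belong. For a subject assigned 320mg who gets 160mg at Baseline and 320mg afterwards, the rules agree if those data stay under the dose received, but differ for the 28 days to Week 4 if they go to the assigned dose.

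**What to change.** Two changes to the SAP:

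- In 8.1.1, replace the last sentence with: *TEAEs will be categorized by PS0011 treatment group, subject to the reallocation rules for misdosed subjects in Section 3.6.* The reallocation rules need to be named, because Section 3.6 contains both the assigned-treatment definition and the exceptions to it.
- In 8.1.3, add: *Where Section 3.6 reallocates a subject from a time point onward, exposure at risk will be split at that date so that events and person-time are in the same treatment group.*

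With both in place, an event and its person-time fall under the same rule, and nothing changes for subjects dosed as assigned. The cost is two sentences and a small programming rule, with no new data.

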8.1.2 Derivation of Duration of Exposure

The duration of exposure (in days) will be calculated as:

$$\begin{aligned} \text{Duration of exposure} \\ = \text{Date of last dose in PS0011} - \text{Date of first dose in PS0011} + 28 \end{aligned} \quad (4)$$

Should the date of the last dose plus 28 days equate to a date that is beyond the Week 48 visit date then the exposure will be calculated as:

$$\text{Duration of exposure} = \text{Week 48 visit date} - \text{Date of first dose in PS0011} \quad (5)$$

For subjects who have died and the date of last dose plus 28 days extends beyond the date of death, the exposure will be as follows:

$$\text{Duration of exposure} = \text{Date of death} - \text{Date of first dose in PS0011} + 1 \quad (6)$$

8.1.3 Derivation of exposure at risk

Throughout this section, date of last clinical contact for each subject is defined as the maximum of [last visit date including SFU visits, last imputed AE start date, date of study termination or completion, last date of study drug administration].

In general, exposure days at risk will be calculated as:

$$\begin{aligned} \text{Exposure days at risk} \\ = \text{Date of last dose in PS0011} - \text{Date of first dose in PS0011} + 140 \end{aligned} \quad (7)$$

Alternatively, for subjects who die or are lost to follow-up prior to the Week 48 visit, total exposure days at risk will be calculated as:

$$\begin{aligned} \text{Exposure days at risk} \\ = \text{Date of last clinical contact in PS0011} - \text{Date of first dose in PS0011} \\ + 1 \end{aligned} \quad (8)$$

For the analysis based on data through to the last Week 48 visit (see [Section 4.3](#)), there may be subjects who are still ongoing in the SFU period at the time of data cut-off. For such subjects, exposure days at risk will be calculated as follows:

$$\text{Exposure days at risk} = \text{Data cutoff date} - \text{Date of first dose in PS0011} + 1 \quad (9)$$

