Investigators should attempt to obtain information on subjects in the case of withdrawal. For subjects considered as lost to follow-up, the Investigator should make an effort (at least 1 phone call and 1 written message to the subject), and document his/her effort (date and summary of the phone call and copy of the written message in the source documents) to complete the final evaluation. All results of these evaluations and observations, together with a narrative description of the reason(s) for removing the subject, must be recorded in the source documents. The eCRF must document the primary reason for withdrawal.

Investigators should contact the Medical Monitor, whenever possible, to discuss the withdrawal of a subject in advance.

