9.1.2 Procedures for reporting and recording AEs

The subject will be given the opportunity to report AEs spontaneously. A general prompt will also be given at each study visit to detect AEs. For example:

“Did you notice anything unusual about your health (since your last visit)?”

In addition, the Investigator should review any self-assessment procedures employed in the study.

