14.3.1 Primary safety analysis

All TEAEs will be summarized descriptively by PS0011 treatment group, primary SOC, high level term (HLT), and preferred term (PT). This summary will include the exposure adjusted incidence rate (EAIR) with associated 95% confidence interval and the exposure adjusted event rate (EAER).

For EAIR, the numerator will be the total number of subjects experiencing the AE. The denominator will be 100 subject-years; that is, the total summation of individual subject-years at risk up to the first occurrence of the AE for subjects with that AE, and the total subject-years at risk for those subjects not experiencing that AE, divided by 100. Exposure adjusted incidence rates will be presented with a 95% exact confidence interval based upon the Chi-Square distribution (Ulm, 1990).

For EAERs, the numerator will be the number of AEs including repeat occurrences in individual subjects; the denominator will be 100 subject-years. That is, the total summation of individual subject-years at risk divided by 100. No confidence interval will be computed for EAER.

Patient exposure at risk in days will be defined as date of last administration of study medication – date of first administration of study medication in PS0011 + 140 days (ie, the duration of the SFU Period). If a subject dies, patient exposure at risk is censored at the date of death. The sum of these exposure days at risk across subjects is converted to years for the EAIR and EAER calculations described above.

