3.9 Analysis time points

3.9.1 Double-blind treatment period

The double-blind treatment period begins at the Baseline visit (Week 0) at the time of first study medication administration (inclusive) and ends at the Week 48/withdrawal visit.

Subjects will be classified as completing the study if they complete the Week 48 visit without withdrawal from the study. This is regardless of whether they attend the SFU visit.

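### SAP 8.1.3 credits 140 days at risk after the last dose even when the Safety Follow-Up visit is missed, so time in which adverse events were not solicited can enter the primary safety denominator

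*SAP*

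**What the plan says.** Protocol 14.3.1 defines exposure at risk as last administration minus "date of first administration of study medication in PS0011 + 140 days (ie, the duration of the SFU Period", and adds: "If a subject dies, patient exposure at risk is censored at the date of death". SAP 8.1.3 eq (7) repeats the 140-day rule as the general case. There are two exceptions:

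- Eq (8): "for subjects who die or are lost to follow-up prior to the Week 48 visit, total exposure days at risk will be calculated as" last clinical contact minus first dose plus 1. Last clinical contact is the latest of "last visit date including SFU visits, last imputed AE start date, date of study termination or completion, last date of study drug administration". No upper limit is set.
- Eq (9): at the Week 48 interim only, subjects still in SFU count to the data cutoff.

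The credit matches the TEAE window in SAP 8.1.1, which runs "through the final administration of study treatment + 140 days (covering the 20-week SFU period". SFU is a planned visit for completers and early withdrawers alike (protocol 6.3, SAP 2.3.2). A subject who reaches Week 48 nevertheless counts as completing the study under SAP 3.9.1: "This is regardless of whether they attend the SFU visit". Adverse events are elicited at visits; protocol 9.1.2 says "A general prompt will also be given at each study visit to detect AEs". Protocol 9.2.2 extends collection for SAEs to 30 days after each subject's end of study, and without time limit for those thought related to study drug.

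**The concern.** Two groups keep the full 140-day credit with no SFU visit behind it: Week 48 completers who skip SFU, and early withdrawers who skip it but are not classed as lost to follow-up (for example after PASI75 non-response or withdrawal of consent). Nobody asks these subjects about events after their last visit. The days enter the EAER denominator (SAP 8.1.5), and the EAIR denominator for subjects without the event (SAP 8.1.4), while most non-serious events in those days cannot reach the numerator. This is the primary safety variable, and the resulting error makes the rates look lower.

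Eq (8) raises two further problems. Read literally, a death after Week 48 falls back to eq (7). Even an earlier death runs to last clinical contact, which a later termination date could push past the date of death. Protocol 14.3.1 censors at death in both cases. Second, the disposition label can change the denominator for the same observed history.

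**Working it through.** **Reproducing the plan's figure.** SAP 7 expects 24 injections, two per dose: 24 / 2 = 12 doses, so the last dose falls on day 11 × 28 = 308 (Week 44). Eq (7): 308 + 140 = 448 days = 64 weeks, the maximum duration in SAP 2.3.3 and protocol 5.1.1.

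**Excess for one subject who misses SFU.** Observed days = last visit − first dose + 1.

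| Subject | Credited, eq (7) | Observed | Excess | Share of credit |
|---|---|---|---|---|
| Completer, last seen Week 48 | 448 | 336 + 1 = 337 | 111 | 24.8% |
| Last dose Week 8, last seen Week 12 | 56 + 140 = 196 | 84 + 1 = 85 | 111 | 56.6% |
| Last dose Week 20, last seen Week 24 | 140 + 140 = 280 | 168 + 1 = 169 | 111 | 39.6% |

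Protocol Table 5-1 appears to mark administration at Week 48, against SAP 7 and protocol 8.8; those passages must be reconciled. With a dose there, the completer's excess would be 139 of 476 days (29.2%).

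**EAER, completers only.** Let f be the share missing SFU. With a constant rate and no late capture, the understatement is f × 111/448, about 0.25% for each 1%. The documents give no f, so these values are assumptions:

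| f | No late capture | Half of late events captured | Rate after Week 48 halved, no late capture |
|---|---|---|---|
| 5% | 1.2% | 0.6% | 0.7% |
| 10% | 2.5% | 1.2% | 1.4% |
| 20% | 5.0% | 2.5% | 2.8% |

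The last column is f × 55.5 / (337 + 55.5), measured against the full-window rate.

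**EAER, with early withdrawers (assumed mixes, constant rate, no late capture).** Last dose at Week 8 for withdrawers.

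- 10% withdraw; 5% of completers and 30% of withdrawers miss SFU: (0.045 + 0.03) × 111 / (0.9 × 448 + 0.1 × 196) = 8.325 / 422.8 = 2.0%.
- 20% withdraw; 10% and 50% miss it: 0.18 × 111 / 397.6 = 5.0%.
- 30% withdraw; 20% and 80% miss it: 0.38 × 111 / 372.4 = 11.3%.

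**EAIR.** With constant hazard h = −ln(1 − p)/448 for cumulative incidence p, f = 10% and no late capture, the understatement is 2.45% at p = 5%, 2.41% at 10%, 2.04% at 50% and 1.48% at 80%.

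**Label dependence.** Last dose Week 8, last seen Week 12, no SFU. Withdrawal of consent gives 196 days by eq (7). Loss to follow-up gives 85 by eq (8) if no later termination date is recorded; 113 or 141 if termination is dated Week 16 or 20; and 29 × 7 + 1 = 204 if dated Week 29, which exceeds the 196-day window.

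**Comparing remedies.** Take f = 10%. Capped time per subject is 0.9 × 448 + 0.1 × 337 = 436.9 days. Errors are relative to the full-window rate:

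| Rate after Week 48; late capture | Eq (7) | Time capped, all events to +140 kept | Time and events both capped |
|---|---|---|---|
| Same; none | −2.5% | 0 | 0 |
| Same; half | −1.2% | +1.3% | 0 |
| Same; full | 0 | +2.5% | 0 |
| Halved; none | −1.4% | +1.1% | +1.1% |
| Halved; half | −0.7% | +1.8% | +1.1% |

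Example (same rate, half captured, all events kept): (0.9 × 448 + 0.1 × 392.5) / 436.9 = 442.45 / 436.9 = 1.013.

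**The case against.** The strongest reply is that eq (7) is the protocol's own definition and not an SAP slip. Its window is the TEAE window, so an event reported at any time in those 140 days counts, and for everyone who attends SFU the rate is correct. That stands: this is a design choice shared by both documents.

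A second reply is that stopping the clock at last contact brings its own bias. If every event to +140 days stays in the numerator while time is cut, the rate is overstated, by 1.3% to 2.5% in the table above once late events are captured. If contact is also extended to the start date of a reported event, follow-up comes to depend on having an event. This stands too, and it determines the form of the remedy: numerator and denominator must stop together, and the protocol rate must stay. Even then, if the off-drug rate is under about 44% of the earlier rate, eq (7) is the closer of the two with no late capture, and capture favours it further.

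Third, the analyses are descriptive and the shift is small beside the exact Poisson limits: 4.80 to 18.39 for 10 subjects with the event (−52%/+84%), 81.4 to 121.6 for 100 (−19%/+22%). True, but interval width does not correct a systematic shift in the estimate.

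Fourth, the 113-, 141- and 204-day examples rest on assumed termination dates. The documents do not say when sites record termination, so these show what eq (8) permits, not what will happen. Protocol 6.3 requires only that "the Investigator should make an effort (at least 1 phone call and 1 written message to the subject".

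**Conclusion.** The point holds as a conditional one. If subjects miss SFU and late non-serious events go unreported, EAER is understated by up to about 0.25% for each 1% of completers who miss it (constant rate, no late capture). An early withdrawer who misses it adds the same 111 days, but to a shorter credited time. The EAIR of less common events is affected similarly, and common events less. The effect is zero with full attendance and smaller for SAEs, which are still collected after the last visit. The conflict over censoring at death is a matter of text and does not depend on attendance.

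A reader might infer four stronger things that the documents do not support:

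- That the effect cannot exceed a few percent. No attendance or withdrawal rate is given, and the assumed mixes above reach 11.3%, so no maximum can be stated.
- That the rates will be understated. This needs missed SFU visits and unreported events, and neither is shown.
- That comparisons between dose groups are distorted. Nothing shows that attendance differs by group.
- That a capped rate should replace the protocol rate. Which of the two is closer depends on the off-drug event rate and late capture, both unknown.

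This is worth correcting because it concerns the primary safety denominator and costs little. Nothing here suggests that it would alter the study's descriptive conclusions.

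**What to change.** 1. Censor every death at its date, before or after Week 48, as protocol 14.3.1 requires.
2. Cap eq (8) at last dose − first dose + 140, and drop the study termination or completion date from last clinical contact.
3. Keep the protocol-defined rates as the main result. Beside them show EAIR and EAER with exposure = min(last dose − first dose + 140, E − first dose + 1). E is the earlier of death and the last visit or contact at which adverse events were solicited; it is not extended by an event's start date. An SFU visit within its −3/+7 day window counts through last dose + 140, so a completer who attends stays at 448 days. Count in this table only events starting on or before E, and list later reported events separately so that none is lost.
4. Leave eq (9) unchanged. Applying E at the interim would cut time for every subject still in SFU, not only for those who miss it.
5. Record in SAP 3.11 the loss-to-follow-up censoring, which protocol 14.3.1 does not contain, and the added analysis.

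The cost is one revised derivation, one extra table with a short listing, and an SAP entry; no new data are needed. In the added table rates will be slightly higher if late events go unreported, and off-drug time gets slightly less weight.
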